Vital signs	X	X	X	X	X					X	X	In the first 6 weeks on study treatment, vital signs are measured as follows: 
 • Predose (within approximately 30 to 60 minutes prior) • 4 hours (\pm1 hour) postdose on Day 1 and Day 8. After 6 weeks, vital signs to be measured predose.
Standard 12-lead ECG	X					X post dosing				X	X	
Triplicate digital ECG		X	X	X								See Table 3 for triplicate ECG details.

Assessments and Procedures	Screen (D -28 to -1)	DLT Period (21 days)					Subsequent 3-week Periods (21 days)			End of Study Intervention Visit	Safety Follow up/ Discontinuation Visit	Notes
Day		1	2	8	9	15	1	8	15	Within 7 days after last dose	30 days after last dose	
Visit Window (days)	-1									+7	+/- 7	Day 1 assessments that could be completed on Day -1 are limited to physical examination, height/weight, and ECOG performance status.
ECOG performance status	X	X					X			X	X	See Appendix 10 .
AE, AESI and SAE assessment	Continuous										From time of signing the ICF through the Safety Follow-up Visit, and until completion of the study. SAEs and AESIs should be followed until resolution, stabilization, the event is otherwise explained, or the participant is lost to follow-up (see Section 8.3.3).	
Concomitant medications and procedures (including collection of subsequent anticancer therapy)												
Serum Chemistry	X	X	X	X		X	X	X	X	X	X	For Visit 1/D1, sample can be collected up to 72 hours prior to dosing. D8 and D15 assessments are optional after Week 9. See Appendix 6 for details.
Hematology and Coagulation (PT, aPTT, INR)	X	X	X	X		X	X	X	X	X	X	For Visit 1/D1, sample can be collected up to 72 hours prior to dosing. D8 and D15 assessments are optional after Week 9. See Appendix 6 for details.
Urinalysis	X	X				X	X			X		See Appendix 6 for details.

Assessments and Procedures	Screen (D -28 to -1)	DLT Period (21 days)					Subsequent 3-week Periods (21 days)			End of Study Intervention Visit	Safety Follow up/ Discontinuation Visit	Notes
Day		1	2	8	9	15	1	8	15	Within 7 days after last dose	30 days after last dose	
Visit Window (days)		-1								+7	+/- 7	Day 1 assessments that could be completed on Day -1 are limited to physical examination, height/weight, and ECOG performance status.

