Plasma – Circulating Tumor DNA Sample		X									Collect predose.
Fresh Paired Tumor Biopsies	X									X	Mandatory collection, if not contraindicated for medical reasons. The first of two paired biopsies must be collected anytime during screening. The second biopsy must be collected on D4 from 2 to 4 hours after study intervention. No bone biopsies are allowed.
Blood - Immune Phenotyping		X									Collect predose.
Serum/plasma – Circulating Factors		X									Collect predose.

AE = adverse event; aPTT = activated partial thromboplastin time; CT = computed tomography; D = Day; DNA = deoxyribonucleic acid; ECG = electrocardiogram; ECOG = Eastern Cooperative Oncology Group; HIV = human immunodeficiency virus; INR = international normalized ratio; MRI = magnetic resonance imaging; Pd = pharmacodynamic; PK = pharmacokinetic; PT = prothrombin time; RDE = recommended dose for expansion; SAE = serious adverse event; WOCBP = woman of childbearing potential.

1.3.3

Parts 1A and 1B – Pharmacokinetic, ECG, and Schedule

CCI

ampling

Table 3

Part 1A M4076 Monotherapy Dose Escalation: Pharmacokinetic, ECG and Assessments

CCI

Study Day	M4076 Dosing	PK Sampling Time	ECG ^b	Paired Biopsies	CCI
Screening (D -28 to -1)				X	
Day 1	X	Predose ^a	X		
		0.5 hour ± 10 minutes postdose			
		1 hour ± 10 minutes postdose			
		2 hours ± 10 minutes postdose	X		
		3 hours ± 20 minutes postdose	X		
		4 hours ± 20 minutes postdose	X		
		6 hours ± 20 minutes postdose	X		
Day 2	X	Predose ^a	X		
		2 hours -4 hours postdose ^c		X ^c	
Day 8	X	Predose ^a	X		
		1 hour ± 10 minutes postdose	X		
		2 hours ± 10 minutes postdose	X		
		3 hours ± 20 minutes postdose	X		

Study Day	M4076 Dosing	PK Sampling Time	ECG ^b	Paired Biopsies	CCl [REDACTED]
		4 hours ± 20 minutes postdose	X		
		6 hours ± 20 minutes postdose			
		8 hours ± 20 minutes postdose	X		
Day 9	X	Predose ^a			
Day 22	X	Predose ^a			X
		2 hours ± 10 minutes postdose			X
		4 hours ± 20 minutes postdose			X
All subsequent Day 1 of every 3 week treatment period	X	Predose ^a			

Note: The fasting window in Part 1A is defined as: 2 hours predose to 1-hour postdose in general, and 2 hours predose to 4 hours postdose on days where PK-time matched triplicate ECG will be collected.

ECG = electrocardiogram; γ-H2AX = gamma histone family member X; CCl [REDACTED]; PK = pharmacokinetic.

^a All predose samples have a window of -60 minutes prior to dosing.

^b The window period for ECG is the same as noted for PK sampling.

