Tumor biopsies	Fresh tumor biopsies are required for subsets of participants as detailed in the Schedule of Activities and inclusion criteria and are considered essential for the study's scientific objectives. Biopsies carry a risk of AEs including bleeding and infection.	Investigators are to use clinical judgement and not proceed with biopsy if high risk of adverse events. Protocol allows omission of biopsies if contraindicated for medical reasons (see Section 8.6).

AE = adverse event; CYP = cytochrome P; ECG = electrocardiogram; IB = investigator's brochure.

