8.3 Adverse Events and Serious Adverse Events

The definitions of an Adverse Event (AE) and a Serious Adverse Event (SAE) are in [Appendix 4](#).

The Investigator and any qualified designees (e.g., Sub-Investigators) are responsible for detecting, documenting, and recording events that meet the definition of an AE or SAE. The Investigator remains responsible for following up AEs that are serious or that caused the participant to discontinue the study intervention or study, as specified in [Section 8.3.3](#).

Requests for follow-up will usually be made via the Study Monitor, although in exceptional circumstances the global patient safety department may contact the Investigator directly to obtain further information or to discuss the event.

The method of recording, evaluating, and assessing causality of AEs and SAEs and the procedures for completing and transmitting SAE reports are in [Appendix 4](#).

8.3.1 Time Period and Frequency for Collecting Adverse Event and Serious Adverse Event Information

All SAEs will be collected from the signing of the ICF until the safety follow-up visit at the time points specified in the Schedule of Activities ([Section 1.3](#)). Beyond this reporting period, any new unsolicited SAEs that the Investigator spontaneously reports to the Sponsor will be collected and processed.

All AEs will be collected from the signing of the ICF until the safety follow-up visit at the time points specified in the Schedule of Activities.

AEs/SAEs that begin before the start of study intervention but after obtaining ICF will be recorded on the Medical History/Current Medical Conditions CRF, not on the AE CRF.

All SAEs will be recorded and reported to the Sponsor or designee immediately and under no circumstance will this exceed 24 hours, as indicated in [Appendix 4](#). The Investigator will submit any updated SAE data to the Sponsor within 24 hours of it being available using the same procedure that was used for the initial report.

Investigators are not obligated to actively solicit AEs or SAEs after the end of study participation. However, if the investigator learns of any SAE, including a death, at any time after a participant has been discharged from the study, and he/she considers the event to be reasonably related to the study intervention or study participation, the Investigator will promptly notify the Sponsor.

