#### **Part 1B- Cross-over design:**

Treatment-emergent AEs (TEAEs) are those events with onset dates on or after the first administration of study intervention in the first food effect assessment period. Any AE occurring before the administration of study intervention on Day 1 of the first food effect assessment period and resolved before administration of study intervention or not worsening after administration of study intervention in the first food effect assessment period will be included in the AE listings, but will not be included in the summary tables (unless otherwise stated). These will be referred to as “pre-treatment” AEs. An AE occurring after administration of study intervention will be counted towards the last treatment received before the onset, even if the event is not resolved at the beginning of the following food effect assessment period. An AE that worsens during a later food effect assessment period will be counted towards both treatments.

In case AE-related dates are partial, the available information will be used in a conservative approach to determine whether the AE is treatment-emergent. All analyses described in Section 15.2 will be based on TEAEs if not otherwise specified. The AE listings will include all AEs (whether treatment-emergent or not). AEs outside the on-treatment period will be flagged in the listings.

Unless otherwise specified, TEAEs will be summarized by number and percentage of participants with the TEAE in the category of interest by primary System Organ Class (SOC) and Preferred Term (PT) in alphabetic order.

Each participant will be counted only once within each SOC or PT. If a participant experiences more than one AE within a SOC or PT for the same summary period, only the AE with the strongest relationship or the worst severity, as appropriate, will be included in the summaries of relationship and severity.

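### Events between consent and first dose are recorded as medical history, so screening-biopsy complications stay off the AE CRF and out of the SAP's pre-treatment AE and SAE listings

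*Protocol*

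**What the plan says.** **Collection period.** Protocol 8.3.1 states "All AEs will be collected from the signing of the ICF until the safety follow-up visit" and, for serious events, "All SAEs will be collected from the signing of the ICF until the safety follow-up visit". The Part 1A Schedule of Activities (Table 1) makes AE, AESI and SAE assessment continuous: "From time of signing the ICF through the Safety Follow-up Visit, and until completion of the study".

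**Where pre-dose events go.** The same section then says that AEs and SAEs beginning after consent but before study intervention "will be recorded on the Medical History/Current Medical Conditions CRF, not on the AE CRF". The sentence names SAEs expressly. It has no exception for serious events or for events caused by a study procedure.

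**SAE reporting.** The next paragraph reads "All SAEs will be recorded and reported to the Sponsor or designee immediately and under no circumstance will this exceed 24 hours". It does not exempt SAEs that occur before dosing.

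**Biopsies.** Protocol Table 5 (section 2.3.1) says "Biopsies carry a risk of AEs including bleeding and infection". For Part 1B, Table 2 says "The first of two paired biopsies must be collected anytime during screening", and collection is mandatory unless medically contraindicated. In Part 1A the paired biopsies are optional, with the first also in screening. A fresh screening sample may be requested there if archival tissue is insufficient or more than 12 months old.

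**SAP.** Section 15.2.1 takes AE information from the Adverse Events Details eCRF page. For Part 1B, section 15.2 keeps pre-dose AEs that resolve, or do not worsen, in the listings but out of the summary tables: "These will be referred to as “pre-treatment” AEs". AE listings are to cover all AEs, treatment-emergent or not. Section 15.3.2 flags SAEs whose onset is outside the on-treatment period.

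**The concern.** The protocol requires a procedure whose risks it names, and schedules that procedure in the one interval whose events are kept off the AE page. A bleed or infection after a screening biopsy would sit beside the participant's pre-existing conditions, with nothing to show that the study caused it. If it persisted after dosing, it would look like a baseline condition.

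At stake is the completeness and attribution of safety data on a study procedure. There is also an internal mismatch: the SAP plans listing entries for pre-treatment events that its source page is told not to hold.

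**Working it through.** The plan states no figure to reproduce. The check sets the passages side by side, with one short count.

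1. **Does the screening biopsy fall in the affected interval?** Yes. Screening runs from Day -28 to Day -1 in Part 1A (28 days) and from Day -28 to Day -8 in Part 1B (21 days; first dose on Day -7). The first biopsy of each pair is placed there in both parts.

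2. **Which biopsies are not affected?** The second of each pair, on Day 2 in Part 1A and Day 4 in Part 1B. These follow dosing, so their complications go on the AE CRF.

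3. **How many biopsies in Part 1B?** The target is 12 participants (Protocol 9.2), with two biopsies each: 12 × 2 = 24. First biopsies: 12/24 = 50%. This count is a guide only. Part 1B is conditional, biopsies may be omitted if contraindicated, and participants may be added to obtain pairs. No count can be given for Part 1A, where the biopsies are optional.

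4. **How many events might be involved?** The documents give no complication rate. Assuming 2% to 10% for illustration: 12 × 0.02 = 0.24 and 12 × 0.10 = 1.2, so roughly none or one event among the Part 1B first biopsies.

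5. **Where does such an event appear?**

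| Output | Non-serious pre-dose event | Serious pre-dose event |
|---|---|---|
| Medical History CRF, tabulated by SOC and PT (SAP 11.2) | Yes | Yes |
| AE CRF | No | No |
| SAP AE and SAE listings drawn from the AE page | No | No |
| 24-hour report to the Sponsor | Not required | Required |
| TEAE tables | No, unless it worsens after dosing | No, unless it worsens after dosing |

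6. **Is the SAE route complete?** Not as written. Appendix 4 makes the electronic data collection tool the primary route, with a paper form as back-up, and expects data supplied with the paper form to agree with the CRF. Neither Appendix 4 nor 8.3.1 says how an SAE barred from the AE CRF enters that tool, or against which page it is reconciled.

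7. **Would moving the event to the AE CRF identify it as biopsy harm?** Not by itself. Causality in Appendix 4 is assessed only against study intervention, so relationship to a procedure has no place to be recorded.

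**The case against.** The strongest defence is that nothing goes unrecorded and no planned estimate changes. The events are entered on the Medical History page and tabulated. One that worsens after dosing becomes a TEAE. The AE summaries are TEAE-based, so pre-dose events would be left out of them in any case. Biopsy safety is not an objective, and complications of the on-treatment biopsy are captured. Appendix 4 ties the definition of an AE to use of study intervention, which may be why the rule was written. Recording detail is also delegated to CRF completion conventions that are not among the documents.

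Most of this stands, and it limits the point to listings and attribution. It does not remove it. Section 8.3.1 itself calls these events AEs and SAEs and collects them from consent, so the Appendix 4 definition does not settle the matter. The SAP's listings are meant to hold entries that the rule keeps off their source page. A medical history table by SOC and PT does not show that an event followed a study procedure.

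A reader might infer more: that serious screening events vanish from safety reporting, or that 8.3.1 gives opposite instructions on whether to report them. The documents do not support that. The 24-hour duty covers every SAE, and collecting from consent, reporting within 24 hours and recording on a different CRF page can coexist. What is missing is the link between the report and the CRF.

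**Conclusion.** The point holds as a data-recording defect. If 8.3.1 is followed as written, complications of the screening biopsy are recorded as baseline history and are absent from the AE CRF. The consent-to-first-dose part of the SAP's AE and SAE listings is then empty. For SAEs there is also an unresolved question of entry and reconciliation, but not a removal of the reporting duty.

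The size is modest. It concerns half of the planned Part 1B biopsies if all 12 pairs are taken, plus an unknown number in Part 1A. The expected event count is about 0.2 to 1.2 in Part 1B under the assumed 2% to 10% rate. DLT, dose-escalation and TEAE results do not depend on it. Nor does it follow that biopsy risk cannot be assessed at all, since the second biopsy of each pair is fully covered.

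The conclusion assumes that sites apply the sentence literally and that the unseen CRF conventions do not already override it.

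**What to change.** In Protocol 8.3.1, limit the Medical History rule to non-serious events that are not related to a protocol-mandated procedure. Record every SAE and every procedure-related AE on the AE CRF from consent, and leave the 24-hour SAE rule as it is.

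Add a way to note relationship to the study procedure, either as a CRF item or in the completion guidance, because Appendix 4 covers only relationship to study intervention. The M4076 relationship should also be completed for these records, since SAP 15.2 treats a missing relationship as related.

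In the SAP, keep these events in the listings as pre-treatment AEs outside the TEAE tables, and say so for Part 1A as well as Part 1B. Ask sites for complete onset dates: SAP 9.8 can move a partial onset date in the month of first dose to the dosing date, which would turn a pre-dose event into a TEAE.

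The cost is one protocol sentence, CRF guidance or one procedure-relatedness item, and a few extra AE records. One limit remains. The SAP analyses AEs in the Safety Analysis Set, so a biopsy complication that prevents dosing would still be outside the listings, though it would be in the AE database.

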8.3.2 Method of Detecting Adverse Events and Serious Adverse Events

At each study visit, the participant will be queried on changes in his or her condition.

Care will be taken not to introduce bias when detecting AEs and/or SAEs. Open-ended and non-leading verbal questioning of the participant is the preferred method to inquire about AE occurrences.

The method of recording, evaluating, and assessing causality of AEs and SAEs and the procedures for completing and transmitting SAE reports are in [Appendix 4](#).

8.3.3 Follow-up of Adverse Events and Serious Adverse Events

After the initial AE/SAE report, the Investigator is required to proactively follow each participant at subsequent visits/contacts. All SAEs and adverse events of special interest (AESIs) (as defined in Section [8.3.6](#)), will be followed until resolution, stabilization, the event is otherwise explained, or the participant is lost to follow-up (as defined in Section [7.3](#)). Reasonable attempts to obtain this information will be made and documented. It is also the Investigator's responsibility to ensure that any necessary additional therapeutic measures and follow-up procedures are performed. Further information on follow-up procedures is in [Appendix 4](#).

8.3.4 Regulatory Reporting Requirements for Serious Adverse Events

Prompt notification by the Investigator to the Sponsor of an SAE (particularly life-threatening and deaths) is essential so that legal obligations and ethical responsibilities towards the safety of participants and the safety of a study intervention under clinical investigation are met.

The Sponsor has a legal responsibility to notify both the local regulatory authority and other regulatory agencies about the safety of a study intervention under clinical investigation. The Sponsor will comply with country-specific regulatory requirements relating to safety reporting to the regulatory authority, Institutional Review Boards (IRB)/Independent Ethics Committees (IEC), and Investigators.

Individual Case Safety Reports will be prepared for suspected unexpected serious adverse reactions (SUSAR) according to local regulatory requirements and Sponsor policy and forwarded to Investigators, as necessary.

An Investigator who receives an Individual Case Safety Report describing a SUSAR or other specific safety information (e.g., Emerging Safety Issue Report, summary or listing of SAEs/SUSARs) from the Sponsor will review and then file it along with the Investigator Brochure in the Investigator's Site File and will notify the IRB/IEC, if appropriate according to local requirements.

In this global clinical multicenter study, the Sponsor is in the best position to determine an unanticipated problem (as defined in US Regulations 21 CFR 312.66). The Sponsor will immediately notify all Investigators of findings that could adversely affect the safety of participants, impact the conduct of the study or alter the IRB's approval/favorable opinion to continue the study. An unanticipated problem is a serious adverse event that by its nature, incidence, severity, or outcome has not been identified in the current version of the risk analysis report, specified in Section 2.3

8.3.5 Pregnancy

- Details of all pregnancies in female participants and, if indicated, female partners of male participants will be collected after the start of study intervention and until 28 days after the last study intervention administration. Inadvertent pregnancies will be followed-up as per local/country (health authorities) guidelines.
- If a pregnancy is reported, the Investigator will inform the Sponsor within 24 hours of learning of the pregnancy and will follow the procedures specified below for collection of pregnancy information.
- Abnormal pregnancy outcomes (e.g., spontaneous abortion, fetal death, stillbirth, congenital anomalies, ectopic pregnancy) are considered SAEs.

Collection of Pregnancy Information

Male participants with partners who become pregnant

- The Investigator will attempt to collect pregnancy information on any male participant's female partner, who becomes pregnant while the participant is in this study. This applies only to participants who receive study intervention.
- After obtaining signed consent from the pregnant female partner directly, the Investigator will record the pregnancy information on the appropriate form and submit it to the Sponsor within 24 hours of learning of the pregnancy. The female partner will also be followed to determine the outcome of the pregnancy. Information on the status of the mother and child will be forwarded to the Sponsor. Generally, the follow-up will be no longer than 6 to 8 weeks following the estimated delivery date. Any termination of the pregnancy will be reported regardless of fetal status (presence or absence of anomalies) or indication for the procedure.

Female Participants who become pregnant

- The Investigator will collect pregnancy information on any female participant who becomes pregnant while she is in the study. The initial information will be recorded on the appropriate form and submitted to the Sponsor within 24 hours of learning of the pregnancy.
- The participant will be followed to determine the outcome of the pregnancy. The Investigator will collect follow-up information on the participant and the neonate, and the information will be forwarded to the Sponsor. Generally, follow-up will not be required for longer than 6 to 8 weeks beyond the estimated delivery date. Any termination of pregnancy will be reported, regardless of fetal status (presence or absence of anomalies) or indication for the procedure.
- While pregnancy itself is not considered to be an AE or SAE, any pregnancy complication or elective termination of a pregnancy for medical reasons will be reported as an AE or SAE.
- A spontaneous abortion (occurring at < 22 weeks gestational age) or stillbirth (occurring at > 22 weeks gestational age) is always considered to be an SAE and will be reported as such.
- Any post-study pregnancy related SAE considered reasonably related to the study intervention by the Investigator will be reported to the Sponsor as specified in Section 8.3.4. While the Investigator is not obligated to actively seek this information in former study participants, he or she may learn of an SAE through spontaneous reporting.
- Any female participant who becomes pregnant while participating in the study will discontinue study intervention.

